6 PHARMACOKINETICS

Plitidepsin pharmacokinetics (PK) will be evaluated in at least 100 patients receiving both plitidepsin and dexamethasone (Arm A) at selected sites. Patients will be sampled during Days 1 and 15 of the Cycle 1 and on Day 1 of the Cycle 2 using a sparse sampling schedule.

In the treatment infusions with blood sampling for pharmacokinetics, the infusion rate will be established so that it ensures that the total plitidepsin dose is infused over 3 hours. Drug will be infused at a constant rate throughout the 3-hour period. In order to obtain reliable pharmacokinetic information, the infusion rate should not be modified once the infusion begins. If a variation in the infusion time eventually occurs, it is very important to reflect it in the CRF, writing clearly the time of the beginning and the end

of the infusion. The infusion rate should not be changed to maintain the scheduled duration of infusion. It would be enough just to record the actual duration in the CRF and in the pharmacokinetic sampling sheet in the cycles in which PK sampling is performed.

Blood samples will be obtained through a peripheral vein located in the contralateral side to that of the infusion. In any case, the sampling vein has to be different to that in which study drug is infused. Even the last sample must never be collected from the infusion catheter. If the blood sample is obtained from a catheter, the first ml of blood will be discarded to avoid the dilution of the sample with the solution used to keep it permeable.

Four-ml blood samples will be collected in sodium heparin tubes. Sample tubes will be gently inverted several times to assure adequate mixing with the heparin and the blood (without centrifugation) should be transferred to the provided polypropylene tubes and stored at -20°C until the shipping to the analysis laboratory. The tubes will be provided by PharmaMar.

A total of 13 blood samples will be collected during the first three infusions (infusions 1 and 2 of Cycle 1, and infusion 1 of Cycle 2) at the time points detailed in Table 5.

Sample	Cycle	Infusion	Time	Time*
number			(from start of each	(relative to EOI)
			infusion)	
1	1	1	0 h	Preinfusion
2	1	1	3 h	Just before EOI
3	1	1	4 h	One hour after EOI
4	1	1	6 h	Three hours after EOI
5	1	2	0 h	Preinfusion
6	1	2	3 h	Just before EOI
7	1	2	4 h	One hour after EOI
8	1	2	6 h	Three hours after EOI
9	2	1	0 h	Preinfusion
10	2	1	3 h	Just before EOI
11	2	1	4 h	One hour after EOI
12	2	1	6 h	Three hours after EOI
13	2	1	~336	Two weeks after EOI**

Table 5. Sampling points for pharmacokinetic evaluations.

*The length of the infusion is three hours.

**Previous to second infusion of the second cycle.

EOI: end of infusion.

The accurate recording of actual dosing and sampling times is much more important than the strict adherence to the scheduled times.

Once all samples from a patient have been collected they should be shipped to the central laboratory for pharmacokinetics as soon as possible, ideally the next shipping day. The time span between the moment the last PK sample for a patient has been collected and the shipment of all the samples from this patient to the central lab should not exceed two months.

Samples will be identified with the following data: study reference, patient number, sample number, date and time of collection. At all time the confidentiality of patient's data will be maintained.

A manual of instructions for sample collection, labeling, storage, and shipment will be provided as a separate document.

7 TREATMENT

7.1 STUDY MEDICATIONS

For information regarding dexamethasone please refer to Dexamethasone Drug Information, provided as a separate document. For detailed instructions regarding plitidepsin inventory, handling, reconstitution, dilution, storage, accountability and disposal, please refer to the updated Aplidin[®] Preparation Guide for Infusion, also provided as separate document.

Commercially available oral dexamethasone formulation will be provided by the Sponsor.

7.1.1 Quantitative and Qualitative Composition

7.1.1.1 *Plitidepsin*

Plitidepsin will be supplied as a powder and solvent for concentrate for solution for infusion. The 2-mg vial should be reconstituted with a 4-ml ampoule of reconstitution solution. The composition of reconstitution solution is Cremophor EL/Ethanol/Water for injection, 15%/15%/70% (v/v/v).

7.2 ADMINISTRATION OF STUDY MEDICATION

The administration of each study medication will be as follows:

- Arm A:
 - a) Dexamethasone: 40 mg orally on Day 1, 8, 15 and 22 every four weeks (q4wk) at least one hour before plitidepsin infusion.
 - b) Plitidepsin: 5 mg/m² intravenously (i.v.) diluted to a total volume of 250 ml in 0.9% saline (or 5% glucose) via a central venous catheter (suggested) or diluted to a total volume of 500 ml in 0.9% saline (or 5% glucose) via a peripheral line. Infusion will be performed through a pump device over three hours (fixed rate) on Day 1 and 15 q4wk.
- Arm B:
 - a) Dexamethasone: 40 mg orally on Day 1, 8, 15 and 22 q4wk.

A cycle is defined as a four-week period.

7.3 CRITERIA FOR TREATMENT CONTINUATION AND RETREATMENT

Patients may be treated with additional cycles of plitidepsin and dexamethasone or dexamethasone alone, as long as no unacceptable toxicity and/or disease progression is documented (see Section 5.2).

Complete blood counts, blood chemistries and other tests will be done prior to starting the next treatment cycle (please refer to Section 5.7 and Section 5.11 for the full list of tests to be done before each drug administration and/or initiation of a new treatment cycle).

Table 6 lists the minimum requirements needed to re-expose the patient to the study drug(s) in each group. Other factors might be considered critical by the Investigator. In this case, these factors should be appropriately documented in the patient's record and on the CRF, and discussed with the Sponsor.

If the criteria listed in Table 6 are not met on the day of the next planned dose, administration of the study drug(s) should be delayed. The criteria for treatment administration should be reevaluated weekly. The new cycle will start upon recovery to the values listed in those tables, for Day 1.

A maximum cycle delay of two weeks is allowed for recovery from drug-related AEs. If no recovery was found after the two-week delay, the patient should discontinue the treatment, except —upon Sponsor's agreement— in cases of obvious patient benefit in continuing the treatment according to the investigator's criteria.

Before the administration of each dose (retreatment), patients must fulfill the baseline criteria defined in Table 6.

Criteria for continuation of treatment	Plitidepsin (Arm A) Day 1 ^a and 15 ^b	Dexamethasone (Arm A and B) Day 1 ^a and 15
ANC	$\geq 1.0 \text{ x } 10^9/\text{l}$ or return to baseline values if extensive BM involvement	-
Platelets	$\geq 50 \times 10^{9}$ /l or return to baseline values if extensive BM involvement	-
Hemoglobin	$\geq 8.5 \text{ g/dl}$	≥ 8.5 g/dl
Direct bilirubin if total bilirubin is above the upper normal limit	≤ 1.0 x ULN	-
AST/ALT	≤ Grade 2	-
Muscular toxicity (myalgia, muscular weakness, CPK increase)	≤ Grade 2	≤ Grade 2
Other non-hematological drug- related AEs (except for increased GGT and/or AP, not optimally treated nausea and vomiting or hypertension, alopecia) ^c	≤ Grade 1	≤ Grade 1

Table 6. Criteria for continuation of treatment

Criteria for continuation of treatment	Plitidepsin (Arm A) Day 1 ^a and 15 ^b	Dexamethasone (Arm A and B) Day 1 ^a and 15
ECG, ECHO/MUGA ^d	Same as baseline	Same as baseline

- a. If a patient does not meet the requirements for treatment continuation on Day 1 of the following cycle, the infusion of study drugs will be withheld until recovery or for a maximum of 14 days. After this period, if delay is due to toxicity assessed as related to study drug, a dose decrease of 20% is mandatory; up to a maximum of two individual dose reductions are allowed. Patients needing additional dose reductions must be withdrawn from the trial.
- b. If a patient does not meet the requirements for treatment continuation on Day 15, the administration of plitidepsin will be omitted. Patients requiring frequent dose omissions may have a dose reduction of 20% upon Investigator and Sponsor agreement. In no case more than two dose reductions are allowed
- c. Any grade accepted for increased GGT and/or AP, and up to grade 2 peripheral neuropathy.
- d. To be performed every three months unless more frequent assessments are clinically indicated.

AEs: adverse event(s); ANC: absolute neutrophil count; AP: alkaline phosphatase; BM: bone marrow; AST/ALT: aspartate aminotransferase/alanine aminotransferase; CPK: creatine phosphokinase; GGT: γ-glutamyltranspeptidase; ECG: electrocardiogram; ECHO/MUGA: echocardiogram/multiple-gated acquisition scan.

7.4 **DOSE REDUCTION CRITERIA**

Patients experiencing frequent dose omissions and/or unacceptable toxicity, defined as

- less than 50% compliance with treatment schedule, and/or
- grade \geq 3 febrile neutropenia, or
- grade 4 neutropenia and infection, or
- grade 4 neutropenia lasting > 7 days (except for patients with extensive BM involvement), and/or
- grade 4 thrombocytopenia (except for patients with extensive BM involvement), and/or
- grade 4 thrombocytopenia with grade ≥ 3 bleeding (in patients with extensive BM involvement), and/or
- any grade ≥ 3 clinically relevant non-hematological toxicity other than non-optimally treated nausea and vomiting, diarrhea lasting < 48 hours and/or grade ≥ 3 asthenia/fatigue lasting < 5 days

may continue treatment after reducing 20% of the dose of plitidepsin (first reduction to 4 mg/m^2 , and second reduction to 3.2 mg/m^2), upon Sponsor agreement, if patient benefit is perceived.

Dexamethasone doses are to be reduced by 50%, up to a maximum of two consecutive dose reductions (first one, 20 mg Days 1,8,15 and 22, and second, 20 mg Days 1 and 15 of each 28-day cycle), if a patient experiences muscular toxicity of grade \geq 3 (weakness, myalgia and/or CPK elevations), or drug-related grade \geq 3 fatigue, or mood disturbances or agitation of grade \geq 2 or grade \geq 3 fluid retention or grade 4 clinically documented infection. These dose reductions are to be implemented independently from plitidepsin dose reductions, if required.

Dose reduction criteria for both study drugs are summarized in Table 7.

Toxicity	Worst grade	Plitidepsin	Dexamethasone
Less than 50% compliance with treatment schedule		Decrease to 4 mg/m^2 , then to 3.2 mg/m^2	No reduction
Febrile neutropenia	≥ 3	Decrease to 4 mg/m^2 , then to 3.2 mg/m^2	No reduction
Neutropenia lasting > 7 days (except for patients with extensive BM involvement)	4	Decrease to 4 mg/m^2 , then to 3.2 mg/m^2	No reduction
Thrombocytopenia (except for patients with extensive BM involvement)	4	Decrease to 4 mg/m^2 , then to 3.2 mg/m^2	No reduction
Thrombocytopenia with grade ≥ 3 bleeding (in patients with extensive bone marrow involvement)	4	Decrease to 4 mg/m^2 , then to 3.2 mg/m^2	No reduction
Any clinically relevant and/or non-hematological toxicity (except non- optimally treated nausea and vomiting, diarrhea < 48 hours and/or asthenia/fatigue lasting < 5 days)	≥ 3	Decrease to 4 mg/m^2 , then to 3.2 mg/m^2	No reduction
Muscular toxicity (weakness, myalgia and/or CPK elevations)	≥3	First episode: decrease to 4 mg/m ² , then reduce dexamethasone; if toxicity recurs, reduce to 3.2 mg/m ²	First reduce plitidepsin; if persistence, decrease dexamethasone to 20 mg Days 1,8,15,22 of each cycle; if toxicity recurs, decrease again plitidepsin and, if persistence, then decrease dexamethasone dose to 20 mg Days 1 and 15 of each cycle. Two dose reductions are allowed for either agent (only for muscular toxicity).
Mood disturbances/agitation	≥2	No reduction	First reduction to 20 mg Days 1,8,15,22 of each cycle, then to 20 mg Days 1 and 15 of each cycle.
Fluid retention	≥ 3	No reduction	First reduction to 20 mg Days 1,8,15,22 of each cycle, then to 20 mg Days 1 and 15 of each cycle.

Table 7. Dose reduction criteria for plitidepsin and dexamethasone.

Toxicity	Worst grade	Plitidepsin	Dexamethasone
Clinically documented infection	4	No reduction	First reduction to 20 mg Days 1,8,15,22 of each cycle, then to 20 mg Days 1 and 15 of each cycle.

Once a dose reduction has been implemented, dose will not be re-escalated thereafter. No more than two dose reductions (of either compound, if required) are allowed. Patients needing additional dose reductions must be withdrawn from the trial.

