Patients will be considered to be **on-study** from the signature of the informed consent to the end of the follow-up period. Patients will be considered to be **on-treatment** for the duration of their treatment and 30 days following the last treatment dose. Those patients in the control arm (Arm B) who **crossed over** to the combination arm (Arm A) after disease progression will be considered on-treatment for the duration of their whole

treatment (dexamethasone alone + dexamethasone in combination with plitidepsin) and during 30 days following the last treatment dose.

Patients may withdraw consent at any time.

5.2 **TREATMENT DISCONTINUATION**

Patients will receive the study drugs while it is considered to be in their best interest. Specifically, treatment will continue until:

- Disease progression (except for those patients treated with dexamethasone alone and eligible to be offered crossover to combination therapy).
- Unacceptable toxicity.
- Intercurrent illness of sufficient magnitude to preclude safety continuation of the study.
- Patient refusal, and/or non compliance with study requirements.
- Protocol deviation with an effect on the risk/benefit ratio of the clinical trial (Section 5.3).
- Treatment delay > 2 weeks from the theoretical treatment date (except in case of clear clinical benefit, with the Sponsors' approval).
- Requirement of > 2 dose reductions of either drug.

Patients who are withdrawn from Arm A for any reasons or from Arm B for any reason other than progression must not be re-treated in the context of this study at any time. For follow-up activities, please refer to Section 5.13.

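### Table 6 footnote a (mandatory 20% decrease after a Day 1 hold) does not fit Sections 5.2, 7.3 and 7.4, and Day 15 dexamethasone has no specific instruction

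*Protocol*

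**What the plan says.** **Day 1, criteria not met.** Table 6 footnote a (Protocol 7.3, repeated in the synopsis table) states that "the infusion of study drugs will be withheld until recovery or for a maximum of 14 days". It continues: "After this period, if delay is due to toxicity assessed as related to study drug, a dose decrease of 20% is mandatory". The marker for this footnote stands on Day 1 of the plitidepsin column and on Day 1 of the dexamethasone column, which is headed for Arms A and B.

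**No recovery after two weeks.** The body of Section 7.3 says: "If no recovery was found after the two-week delay, the patient should discontinue the treatment". An exception follows for obvious benefit, with the Sponsor's agreement. Section 5.2 lists as a reason to stop treatment: "Treatment delay > 2 weeks from the theoretical treatment date", again with a Sponsor-approved exception for clear clinical benefit.

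**Day 15.** For any planned dose on which the criteria fail, the general sentence in Section 7.3 says that "administration of the study drug(s) should be delayed". Footnote b, marked only on the plitidepsin column, says: "If a patient does not meet the requirements for treatment continuation on Day 15, the administration of plitidepsin will be omitted". Day 15 in the dexamethasone column has no footnote.

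**Size of reductions.** Section 7.4 reduces plitidepsin by 20% (to 4, then 3.2 mg/m²). For dexamethasone it says: "Dexamethasone doses are to be reduced by 50%, up to a maximum of two consecutive dose reductions". Table 7 gives the same dexamethasone levels.

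**The concern.** Footnote a is the most specific text on what follows a held Day 1 dose, and it appears in both places where sites look for the retreatment criteria. Read alone, it tells a site to restart at a lower dose. Read with Sections 7.3 and 5.2, the same patient may have to stop unless the Sponsor agrees otherwise. Read on the dexamethasone column, it asks for a step that the dose-reduction section does not contain.

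Three things are at stake.

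- **Irreversible outcomes.** Under Section 5.2, a patient withdrawn from Arm A for any reason, or from Arm B for a reason other than progression, may not be re-treated in the study. An Arm B patient stopped for delay therefore loses access to crossover.
- **Deviation coding.** Section 5.3 treats failure to follow dose-adjustment specifications as a deviation that may affect risk/benefit, and SAP 8.4 plans an analysis of retreatment restrictions. Neither can be coded consistently if the rule is unclear.
- **Exposure tables.** The SAP tabulates dose intensity (8.2), delays over 14 days (Table 12.1.2.1.4), dose reductions in delayed cycles for both arms (Table 12.1.2.2.2) and omissions (12.1.3). Their meaning depends on which instruction was in force.

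**Working it through.** The check is mainly a side-by-side reading, with arithmetic for the dose steps.

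**1. Reproducing the stated dose ladders (Section 7.4, Table 7).**

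- Plitidepsin, 20% steps: 5 × 0.8 = 4.0 mg/m²; 4.0 × 0.8 = 3.2 mg/m². This matches.
- Dexamethasone per 28-day cycle: 4 × 40 = 160 mg; 4 × 20 = 80 mg; 2 × 20 = 40 mg. Each step is 1 − 80/160 = 1 − 40/80 = 50%. This matches.

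**2. Applying footnote a to dexamethasone as marked.**

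- First step: 0.20 × 40 = 8 mg, leaving 32 mg per dose, or 4 × 32 = 128 mg per cycle.
- Second step: 32 × 0.8 = 25.6 mg per dose, or 4 × 25.6 = 102.4 mg per cycle.
- The stated ladder is 160, 80 and 40 mg per cycle. Neither 128 nor 102.4 is on it, so the 20% and 50% rules cannot both set the dexamethasone dose.

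**3. Where the two dexamethasone rules meet or leave a gap.**

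- Table 6 blocks dexamethasone for muscular toxicity above grade 2. Grade 3 or higher muscular toxicity is also a trigger for the 50% step in Section 7.4. A Day 1 hold for this reason falls under both rules.
- Table 6 also blocks dexamethasone for hemoglobin below 8.5 g/dl and for most other drug-related non-hematological events above grade 1. Several of these are not dexamethasone triggers in Section 7.4. If such a hold is drug-related, footnote a alone would call for a decrease.

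**4. Three readings of footnote a by timing.**

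| Reading of footnote a | Sections 7.3 and 5.2 for the same patient |
|---|---|
| Any drug-related hold that ends in recovery within 14 days | Restart allowed; no reduction mentioned there |
| Only patients still unrecovered at the limit but continued by exception | Sponsor agreement required; footnote a does not mention it |
| All patients still unrecovered at the limit | Discontinue unless the exception applies; direct conflict |

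The footnote does not say which reading is meant.

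**5. Day 15.**

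- Plitidepsin: the general sentence says delay and footnote b says omit. The text after the general sentence concerns the next cycle: "The new cycle will start upon recovery to the values listed in those tables, for Day 1". SAP 8.2 counts delays on Day 1 infusions and skipped infusions on Day 15.
- Dexamethasone: only the general delay sentence applies. The note to SAP Listing 12.1.3.2 nevertheless provides for doses skipped on Days 8, 15 or 22.

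**The case against.** Five arguments can be made for the text as it stands.

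- **The passages can be read together.** Sections 7.3 and 5.2 decide who continues, and footnote a sets the dose of those who restart. A reader might infer that sites were free to choose between stopping and reducing. The documents do not support that, because continuation beyond two weeks needs the Sponsor's agreement. This narrows the conflict but does not remove it, since footnote a mentions neither recovery as a condition nor the exception.
- **Footnote a was meant for plitidepsin.** It speaks of an infusion, dexamethasone is oral, and Section 7.4 ties 20% to plitidepsin. That is plausible. But the marker is on the dexamethasone column in both the body and the synopsis, and Arm B receives only oral dexamethasone before any crossover. No passage states a 32 mg dose. Nor does a delay by itself lead to 20 mg, because the 50% step is triggered by listed toxicities.
- **Day 15 plitidepsin is largely settled.** It is tempting to read delay against omission as an open contradiction. Footnote b, the next-cycle wording and SAP 8.2 all point to omission as the intended text. What stands is the unrestricted general sentence and the missing dexamethasone instruction.
- **PFS is little affected.** A reader might infer that stopping treatment breaks PFS follow-up. Protocol 8.1 and SAP 6.1.2 continue four-weekly disease assessments after treatment ends without progression. Section 5.13 does stop marrow, radiological and skeletal evaluations, although the schedule of assessments keeps radiology for truly non-secretory patients assessable only by plasmacytomas. Some effect is possible, but nothing in the documents sizes it.
- **Little is left to correct prospectively.** The protocol records one patient still on treatment on 19 May 2017. This stands, and it shifts the remedy toward documentation.

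**Conclusion.** The inconsistency is real, sits in the current text and is limited in reach. Three items remain.

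1. Footnote a does not say how its mandatory decrease relates to the discontinuation rule and the Sponsor-agreed exception.
2. As marked, it assigns dexamethasone a 20% step (32 mg) that is off the 50% ladder.
3. Day 15 dexamethasone has only the general delay sentence, which also overlaps with footnote b for plitidepsin.

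Item 2 rests on the column marker being intended. If it is a slip, the correction is to the marker.

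A reader might infer that every drug-related delay and every failed Day 15 check is affected. That goes too far. Reach under item 1 depends on the reading taken, Day 15 plitidepsin is largely resolved, and the documents give no count of affected patients. None of these rules enters the sample-size calculation, so power and the 210-event PFS target are unaffected. The consequence lies in exposure summaries, deviation coding and individual withdrawals.

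**What to change.** Reconcile Section 5.2, Section 7.3, Table 6 footnotes a and b with their column markers, Section 7.4 with Table 7, and the matching synopsis text, so that one instruction applies to each drug and each dosing day. The revised text should state:

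- whether footnote a concerns recovery within 14 days, continuation by exception beyond it, or both;
- whether its 20% sentence covers dexamethasone;
- what applies to Day 15 dexamethasone;
- how far the general delay sentence extends, given footnote b.

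Because treatment is nearly complete, also document which reading sites were told to apply and from when. Classify retreatment deviations, delays, reductions and omissions by that reading in the SAP outputs. If sites were told different things, say so in the report.

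The cost is a wording amendment, a note to file and a review of affected delay and dose records. No new data or change to the primary analysis is needed. No dose or clinical rule is proposed here; that choice belongs to the sponsor and its clinical team.

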	 drug, a dose decrease of 20% is mandatory; up to a maximum of two individual dose reductions are allowed. Patients needing additional dose reductions must be withdrawn from the trial. b. If a patient does not meet the requirements for treatment continuation on Day 15, the administration of plitidepsin will be omitted. Patients requiring frequent dose omissions may have a dose reduction of 20% upon Investigator and Sponsor agreement. In no case more than two dose reductions are allowed. c. Any grade accepted for increased GGT and/or AP, and up to grade 2 peripheral neuropathy. d. To be performed every three months unless more frequent assessments are clinically indicated. AEs: adverse event(s); ANC: absolute neutrophil count; AP: alkaline phosphatase; BM: bone marrow; AST/ALT: aspartate aminotransferase/alanine aminotransferase; CPK: creatine phosphokinase; GGT: γ-glutamyltranspeptidase; ECG: electrocardiogram; ECHO/MUGA: echocardiogram/multiple-gated acquisition scan.
Dose reduction criteria	Patients experiencing frequent dose omissions and/or unacceptable toxicity, defined as
	 less than 50% compliance with treatment schedule, and/or grade ≥ 3 febrile neutropenia, or grade 4 neutropenia and infection, or grade 4 neutropenia lasting > 7 days (except for patients with extensive BM involvement), and/or
	• grade 4 thrombocytopenia (except for patients with extensive BM involvement), and/or
	• grade 4 thrombocytopenia with grade \geq 3 bleeding (in patients with extensive BM involvement), and/or
	 any grade ≥ 3 clinically relevant non-hematological toxicity other than non-optimally treated nausea and vomiting, diarrhea lasting < 48 hours and/or grade ≥ 3 asthenia/fatigue lasting < 5 days,
	may continue treatment after reducing 20% of the dose of plitidepsin (first reduction to 4 mg/m ² , and second reduction to 3.2 mg/m ²), upon Sponsor agreement, if patient benefit is perceived.
	Dexamethasone doses are to be reduced by 50%, up to a maximum of two consecutive dose reductions (first one, 20 mg Days 1,8,15 and 22, and second, 20 mg Days 1 and 15 of each 28-day cycle), if a patient experiences
	 muscular toxicity of grade ≥ 3 (weakness, myalgia and/or CPK elevations), or
	 drug-related grade ≥ 3 fatigue, or mood disturbances or
	• agitation of grade ≥ 2 or
	 grade ≥ 3 fluid retention or grade 4 alignically documented infaction

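### Section 7.4 text and Table 7 give conflicting dose-reduction rules for muscular toxicity, fatigue, and grade 4 neutropenia with infection

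*Protocol*

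**What the plan says.** Protocol Section 7.4 gives the reduction rules twice, in prose and in Table 7. The synopsis carries copies of both.

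- **Muscular toxicity, grade 3 or higher.** The prose lists it among the events for which dexamethasone is halved, and closes that list with "These dose reductions are to be implemented independently from plitidepsin dose reductions, if required". The dexamethasone column of Table 7 reads "First reduce plitidepsin; if persistence, decrease dexamethasone to 20 mg Days 1,8,15,22 of each cycle".
- **Fatigue.** The prose list of dexamethasone triggers includes, in the synopsis wording, "drug-related grade ≥ 3 fatigue, or mood disturbances or". Table 7 has no fatigue row of its own. The nearest is "Any clinically relevant and/or non-hematological toxicity (except non- optimally treated nausea and vomiting, diarrhea < 48 hours and/or asthenia/fatigue lasting < 5 days", at grade 3 or higher. There plitidepsin is reduced and dexamethasone is not.
- **Neutropenia with infection.** The prose list of plitidepsin triggers includes "grade 4 neutropenia and infection, or". The grade 4 neutropenia row in Table 7 is limited to "Neutropenia lasting > 7 days (except for patients with extensive BM involvement". The grade 4 row "Clinically documented infection" reduces dexamethasone and leaves plitidepsin unchanged.

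Under Section 7.2, Arm B receives only "Dexamethasone: 40 mg orally on Day 1, 8, 15 and 22 q4wk". Section 7.4 presents Table 7 as a summary of the prose and gives no order of precedence.

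**The concern.** A site that meets one of these events finds two instructions that cannot both be obeyed. The event is not remote: Section 1.3.4.2.1 describes muscular events with CPK increases as the main dose-limiting toxicities of plitidepsin, and Section 1.5.1.1 reports slightly more muscular events once dexamethasone was added.

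The choice of passage has consequences. Section 7.4 forbids re-escalation, allows at most two reductions and withdraws patients who need more, so the rule followed can affect both later dose and time on treatment. Section 5.3 counts plitidepsin dosing that ignores the dose-adjustment rules among the deviations that might affect risk and benefit. For neutropenia with infection, the same action can comply with the prose and depart from the table. Dexamethasone is also the drug common to both arms, so unequal handling between sites or arms would make the dexamethasone exposure tables harder to interpret.

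**Working it through.** The check is a side-by-side reading, plus the dose arithmetic.

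| Event | Section 7.4 prose | Table 7 | Result |
|---|---|---|---|
| Muscular toxicity, grade 3 or higher | Halve dexamethasone, independently of plitidepsin | Plitidepsin first; dexamethasone only if toxicity persists | Conflict on dexamethasone |
| Drug-related fatigue, grade 3 or higher, 5 days or more | Halve dexamethasone | General non-hematological row: dexamethasone unchanged | Conflict on dexamethasone |
| Same fatigue, under 5 days | Halve dexamethasone (no duration limit) | Excepted from the general row; no other row | Missing from table |
| Grade 4 neutropenia with infection | Reduce plitidepsin | No row; grade 4 infection row leaves plitidepsin unchanged | Plitidepsin trigger missing, and at odds with the infection row |
| Grade 4 clinically documented infection, dexamethasone | Halve | First reduction step | Agree |

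**Muscular row.** It is also not consistent within itself. Its plitidepsin column says to reduce plitidepsin and then dexamethasone, without the persistence condition that stands in the dexamethasone column. In Arm B the first step cannot be performed. The prose rule can be applied there, because it does not refer to plitidepsin.

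**Neutropenia with infection.** Some such patients may be caught by the febrile neutropenia row or by the row for neutropenia beyond 7 days. The prose lists all three as separate triggers, so the table still omits one.

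**Dose levels.** These agree between prose and table.
- Plitidepsin: 5 × 0.8 = 4.0 mg/m², then 4 × 0.8 = 3.2 mg/m².
- Dexamethasone per 28-day cycle: 40 × 4 = 160 mg at the start, 20 × 4 = 80 mg after one reduction, 20 × 2 = 40 mg after two.

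The conflict is therefore in triggers and order.

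**Size for a first episode.**
- Muscular toxicity in Arm A: the prose gives 80 mg per cycle; Table 7 gives 160 mg unless toxicity persists.
- Fatigue of 5 days or more, either arm: the prose gives 80 mg; Table 7 gives 160 mg.
- Ratio: 160 / 80 = 2.
- Against the intended 40 mg/week in SAP Section 8.2: 80 / 4 = 20 mg/week, or 50% relative dose intensity, versus 160 / 4 = 40 mg/week, or 100%.

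**When the difference takes effect.** For dexamethasone in both arms, Table 6 requires muscular toxicity to be no worse than grade 2 and other drug-related non-hematological events no worse than grade 1 (with listed exceptions). Otherwise dosing is delayed. Its column names Days 1 and 15, while the Section 7.3 text applies the criteria before each dose. The conflict therefore mainly concerns the dose given when treatment resumes.

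**The case against.** The best defence has four parts.

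1. Table 6 stops dosing during active toxicity, so Table 7 does not simply keep full-dose dexamethasone running through a grade 3 event. This stands, at least for Days 1 and 15, and it limits the safety argument to the dose on resumption.

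2. The prose gives a complete muscular-toxicity rule for anyone taking dexamethasone, and the mood, fluid-retention and infection rows of Table 7 work in Arm B. This also stands. A reader might infer that Table 7 leaves Arm B without any workable rule; only the muscular row fails there.

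3. Independence in the prose may mean only that reductions of the two drugs are counted separately. This does not rescue the table, which makes a dexamethasone reduction wait for a plitidepsin reduction, and it does not touch fatigue.

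4. A reader might infer that the conflict confounds the PFS comparison by keeping dexamethasone higher in Arm A. That direction requires Arm A to follow the table and Arm B the prose, and no passage establishes such a split. The primary endpoint is ITT PFS by a blinded IRC, assessed on the same schedule in both arms irrespective of delays or omissions. Dose reductions for toxicity after randomization are part of the treatment received, not a baseline confounder. SAP Tables 12.1.1.1, 12.1.4.2 and 12.1.4.3 would show dexamethasone intensity and reductions by arm. Confounding is not shown.

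**Conclusion.** The inconsistency holds. Prose and table conflict on dexamethasone for muscular toxicity and for fatigue. They disagree on plitidepsin for grade 4 neutropenia with infection, and the muscular row cannot be applied literally in Arm B. For the same first episode, two sites could resume dexamethasone at doses per cycle that differ two-fold.

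The size rests on a patient starting at full dose and, for muscular toxicity in Arm A, on toxicity that does not persist; if it persists, both routes reach 20 mg per administration. Section 7.4 does not define persistence.

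Two wider readings are not supported. Neutropenia with infection is not a dexamethasone conflict, since prose and table agree on dexamethasone for grade 4 infection. Nor is every patient with severe muscular toxicity or fatigue affected: the fatigue trigger is limited to drug-related events, and the documents give no rates for this regimen. The nearest figure, eight grade 3 or higher muscular events with n=87 in Section 1.3.4.2.1, comes from 1-hour infusion trials. An effect on PFS cannot be quantified.

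The prospective reach is small. Accrual had ended two years before 19 May 2017, and the note to Table 4 records one patient still on treatment on that date. The point now matters chiefly for classifying deviations and for reading the dexamethasone exposure tables.

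**What to change.** Reconcile Section 7.4, Table 7 and both synopsis copies so that:

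- each trigger has one instruction per drug;
- the muscular-toxicity entry can be applied in Arm B, and its two columns agree;
- fatigue, including its duration limit, and grade 4 neutropenia with infection read the same in prose and table;
- it is stated which passage prevails if they differ.

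Which clinical rule to adopt is for the sponsor.

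For patients already treated, the study report should say which passage was used to classify dose-reduction deviations. The cost is protocol wording and a note to sites; sample size and the primary analysis are unaffected.
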